10. STATISTICAL ANALYSES

10.1 Overview

This is an Asian multi-regional clinical trial (MRCT) in which ATG-008 will be administered orally to hepatitis B positive (HBV+) HCC subjects who have received at least one prior line of systemic therapy.

According to the previous study results, the sponsor will plan to continue to enroll approximately 40 hepatitis B virus (HBV) positive, unresectable HCC subjects who have received at least one prior line of systemic therapy. Among which, approximately 20 subjects will receive oral ATG-008 at an initial dose of 45 mg/QD and another 20 subjects will receive oral ATG-008 at an initial dose of 20 mg/BID. The pharmacokinetic (PK) samples will be collected from 10 subjects each in the two dose groups so as to further evaluate the PK profile of ATG-008 and its metabolites.

If ORR of tumor is greater than 15% in the study dose group (45 mg/QD or 20 mg/BID), this study will be expanded to enroll additional approximately 110 subjects using ORR as the primary study endpoint, to further evaluate the efficacy and safety of ATG-008.

It is designed as an open-label phase 2 trial evaluating the pharmacokinetics (PK), tolerability and efficacy of oral ATG-008 administered daily until the radiologic disease

progression (according to RECIST 1.1) or intolerable toxicity.

The sections below provide an overview of the proposed statistical considerations and analyses. The final statistical analysis methods will be documented in detail in the Statistical Analysis Plan (SAP).

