10.3 Sample Size and Power Considerations

For the primary efficacy endpoint, ORR, the sample size is based on one-sample binomial test with normal approximation. The null hypothesis to be tested is that the ORR (defined as the proportion of subjects with at least a partial response (PR) based on the Treated population subjects) is $\leq 10\%$; the alternative hypothesis is that the ORR is $\geq 18\%$. With these hypotheses, a sample size of 130 (20+110) subjects in the Treated population would provide 80% power at a one-sided 0.025 significance level. This criterion requires that the lower limit of the 95% confidence interval (CI) for the ORR is greater than 10%.

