10.6.1 Analysis of the Primary Efficacy Endpoint

Overall response rate (ORR) is the primary efficacy endpoint. A responder is any subject who achieves a CR or PR. ORR is defined as the percentage of subjects that achieve a CR or PR.

ORR will be summarized with 95% confidence interval (CI), and tested using one sample binomial test for the Treated population analyzed in a similar way as for DCR. Subgroup analysis for ORR will be performed for subgroups specified in Section 10.6.3.

ORR with 95% confidence intervals will also be provided for the per-protocol population.

The primary analysis for ORR will be performed at approximately 3 months after the last subject is first dosed. All other endpoints will be analyzed at the same time. The analysis will be updated at 12 months after the last subject's first dose date.

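### If the trial expands, the pooled ORR out of 130 includes the 20 subjects whose high response rate triggered expansion, so the simple proportion is biased upward by about 1 to 2 points; the pooled test itself is sound.

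*Combined protocol and SAP*

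**What the plan says.** Section 10.1 describes two new dose groups: "approximately 20 subjects will receive oral ATG-008 at an initial dose of 45 mg/QD and another 20 subjects" on 20 mg twice daily. It then sets the expansion rule: "If ORR of tumor is greater than 15% in the study dose group" (either of the two), about 110 more subjects are enrolled, with ORR as primary endpoint.

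Section 10.3 counts the triggering subjects in the final analysis: "a sample size of 130 (20+110) subjects in the Treated population". The null is an ORR of at most 10%, the alternative at least 18%, and this size "would provide 80% power at a one-sided 0.025 significance level". Success requires that "the lower limit of the 95% confidence interval (CI) for the ORR is greater than 10" percent.

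For the analysis, Section 10.6.1 states: "ORR will be summarized with 95% confidence interval (CI), and tested using one sample binomial test", on the Treated population. By Section 10.2.1 that population is everyone dosed, so the first-stage subjects stay in. The CI method is not named. No two-stage estimate, adjusted interval or separate result for the 110 is described. Section 10.1 leaves the final methods to a SAP, and nothing in the supplied text covers the matter.

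**The concern.** A result out of 130 exists only if the first 20 passed the 15% rule. Since 3/20 is exactly 15%, passing means at least 4 responders. Reporting x/130 as one simple sample treats those 20 as if they had not been chosen for their result. The expanded ORR and its lower limit are the figures on which ATG-008 would be assessed, and the whole planned difference is only 8 points (10% versus 18%). An upward shift of 1 to 2 points therefore deserves to be visible to the reader.

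**Working it through.** **The plan's own figure.** With the normal approximation named in Section 10.3, n = [(1.96·√(0.10·0.90) + 0.8416·√(0.18·0.82)) / 0.08]² = 129.8, rounded up to 130, with power 80.1%. The stated size is correct.

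**Inputs.** First stage 20 per dose group and expansion 110 (Sections 10.1 and 10.3); expansion if X1 ≥ 4. Assumptions: exactly these sizes, the same true ORR p in both stages, and the same response reading for the expansion decision and the final analysis.

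**Bias given expansion.** X1 ~ Bin(20, p) restricted to X1 ≥ 4, and X2 ~ Bin(110, p). Only the first 20 are affected, so

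bias of x/130 = (20/130) × (E[X1/20 | X1 ≥ 4] − p).

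- p = 18%: (20/130) × (25.0 − 18) = +1.1 points
- p = 15%: (20/130) × (23.8 − 15) = +1.35, about +1.4 points
- p = 10%: (20/130) × (22.2 − 10) = +1.9 points

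**Lower limit.** The mean Clopper-Pearson lower limit moves up by 0.9 points at p = 18% and 1.4 at p = 10%. The table gives the chance that the lower 95% limit exceeds the true ORR, by exact enumeration (nominal 2.5%).

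| True ORR | Chance one group expands | Clopper-Pearson | Wilson | Wald |
|---|---|---|---|---|
| 10% | 13.3% | 6.4% | 10.7% | 3.6% |
| 15% | 35.2% | 3.5% | 5.8% | 3.5% |
| 18% | 49.7% | 3.7% | 5.9% | 2.3% |

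Without selection, Clopper-Pearson gives 1.9%, 1.7% and 2.2%.

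**Sensitivity to first-stage size.** The protocol says approximately 20. With 19 subjects, 3/19 (15.8%) passes. The bias is then (19/129) × (22.4 − 18) = +0.65 at 18% and (19/129) × (18.7 − 10) = +1.3 at 10%, and the Clopper-Pearson rate at 18% falls to 2.7%. With 22 subjects that rate is 2.6%.

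**At the success boundary.** For a total of t responders, the conditionally unbiased estimate is

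Σ C(20,k)·C(110,t−k)·(t−k)/110 ÷ Σ C(20,k)·C(110,t−k), summed over k from 4 to 20.

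The smallest successful count is 20 with Wilson, 21 with Clopper-Pearson and 22 with Wald. At 21/130 the simple ORR is 16.2% and the conditional estimate 14.8%; at 25/130 they are 19.2% and 18.2%. The Clopper-Pearson lower limit at 21/130 is 10.3%. The exact lower limit conditional on expansion is 8.9% at 21, 9.6% at 22 and 10.3% at 23.

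**Overall type I error at p = 10%.** Counting non-expansion as failure, the Clopper-Pearson boundary (21/130) gives 0.85% for one group and 1.6% if the better of two is taken forward. At the Wilson boundary (20/130) the figures are 1.4% and 2.7%, against 3.4% for 130 subjects with no expansion rule. The small excess over 2.5% comes from the approximation; the rule itself lowers the risk.

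**The case against.** The strongest reply is that the pre-specified inference is the test, and the expansion rule makes that test more conservative. This stands, and it is the reason to keep the pooled test. A reader might infer from the conditional lower limits of 8.9% and 9.6% that success at 21 or 22 responders would be a false claim. The error rates do not support that: over all trials started, the type I error is not inflated by pooling.

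A second tempting inference is that the lower limit always exceeds the truth more than 2.5% of the time. It does not follow from the documents. The only approximation that Section 10.3 mentions concerns the sample size, no interval is named, and with Wald the rate at the design alternative is 2.3%. With 19 or 22 first-stage subjects the Clopper-Pearson rate at 18% is also close to nominal.

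Third, the upward bias holds only given expansion. Averaged over stopped and expanded trials, the simple proportion is biased downward (15.1% at a true 18%). The largest effects occur at a true 10%, where one group passes only 13.3% of the time. At 18% the bias is about a third of the standard error (√(0.18·0.82/130) = 3.4 points).

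Fourth, Section 6.4.1 has investigators assess response and also plans central review of all scans, without saying which reading drives expansion or the final ORR. If they differ, the selection effect is diluted, though not removed while the readings are correlated.

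Finally, the later SAP might deal with all this. That is possible, but only the supplied text can be assessed.

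**Conclusion.** The point holds as a matter of conditional estimation. In a trial that expands, x/130 as a simple proportion overstates the ORR by about 1.1 points at a true 18%, 1.4 at 15% and 1.9 at 10%, given exactly 20+110 subjects, a threshold of 4/20 and one reader throughout. With 19 first-stage subjects the figures are 0.65 at 18% and 1.3 at 10%. The lower limit is shifted upward under all three interval methods, but whether its miss rate breaches 2.5% depends on the method and the actual first-stage size. The planned size and the pooled test are not in question. This is a cheap improvement to reporting; it does not correct a wrong decision rule.

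**What to change.** In Section 10.6.1, or in the SAP before expansion data are seen:

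1. Keep the pooled test and name the CI method, for example Clopper-Pearson.
2. Add as supportive (a) the conditionally unbiased two-stage estimate, using the actual first-stage size and the reading that decided expansion.
3. Add as supportive (b) the ORR with exact 95% CI in the expansion subjects alone. This interval is free of both the expansion rule and any choice of dose group.
4. State that (a) does not correct for choosing between two passing dose groups. If the better of two equal groups is taken, the residual bias is about 0.2 points or less at the planning ORRs (10% to 18%).

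The cost is a few lines of text and code. Estimate (a) will be about 1 point below the pooled ORR. The interval in (b) is slightly wider: at 18%, 1.96·√(0.18·0.82/110) = ±7.2 points, against ±6.6 with 130. Result (b) should remain supportive: as the primary analysis with the exact criterion (at least 19/110), its power at 18% would be 61.7%. Naming Clopper-Pearson also fixes the boundary at 21/130. For 130 subjects without the expansion rule, the chance of success at 18% is then 74.2%, against 81.2% at 20/130, so the method should be chosen with that in view.

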10.4 Background and Demographic Characteristics

Subject age, height, weight, and baseline characteristics will be summarized using descriptive statistics, while gender, race and other categorical variables will be provided using frequency tabulations.

Medical history data will be summarized using frequency tabulations by system organ class and preferred term.

Background, demographic characteristics, and medical history will be summarized using both Treated and per-protocol populations.

10.5 Subject Disposition

Subject disposition (analysis population, entered, discontinued, along with primary reason for discontinuation) will be summarized using frequency and percent. A summary of subjects enrolled by site will be provided. Protocol deviations will be summarized using frequency tabulations.

Subject disposition and protocol deviations will be summarized using both Treated and per-protocol populations.

10.6 Efficacy Analysis

All efficacy results will be summarized for the Treated population as the primary analysis. The primary and secondary efficacy endpoints will also be analyzed using the per-protocol population as supportive analysis. Subgroup and exploratory efficacy analyses will be conducted using only the Treated population.

10.6.1 Analysis of the Primary Efficacy Endpoint

Overall response rate (ORR) is the primary efficacy endpoint. A responder is any subject who achieves a CR or PR. ORR is defined as the percentage of subjects that achieve a CR or PR.

ORR will be summarized with 95% confidence interval (CI), and tested using one sample binomial test for the Treated population analyzed in a similar way as for DCR. Subgroup analysis for ORR will be performed for subgroups specified in Section 10.6.3.

ORR with 95% confidence intervals will also be provided for the per-protocol population.

The primary analysis for ORR will be performed at approximately 3 months after the last subject is first dosed. All other endpoints will be analyzed at the same time. The analysis will be updated at 12 months after the last subject's first dose date.

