3. STUDY ENDPOINTS

3.1 Primary Endpoint

- C_{max} , AUC, t_{max} , $T_{1/2}$, CL/F and Vd/F of ATG-008 and M1 after single and multiple doses.
- The incidence of treatment emergent adverse events (TEAEs), SAEs, laboratory abnormalities and other safety parameters
- ORR: Percentage of subjects with PR, or CR

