6.4.1 Assessment of Radiologic Response According to RECIST 1.1

Response will be assessed using RECIST 1.1 Appendix. Response assessments (tumor evaluations) include computed tomography (CT) scan or magnetic resonance imaging (MRI). The regions to be imaged are the chest, abdomen and pelvis, as well as any other region clinically indicated for tumor imaging. Subjects with brain metastases will have brain scans at Screening and at each tumor reassessment. The same mode of imaging for lesion evaluation at screening must be consistently used throughout the study.

The CT imaging should include contrast unless medically contraindicated. Conventional CT should be performed with contiguous cuts of 5 mm or less in slice thickness. Spiral CT should be performed by use of a 5 mm contiguous reconstruction algorithm.

All subjects with evidence of radiologic tumor response (CR or PR) should have the response confirmed with repeat assessments at the next scheduled scan, but after no less than 28 days. Response assessments must have occurred \geq 5 weeks from the first dose date to be considered as SD for a best response.

The Investigators will evaluate RECIST 1.1 response after each restaging and overall assessment. All related scans will be collected and saved for future independent central review.

If ORR of tumor is greater than 15% in the study dose group (45 mg/QD or 20 mg/BID), then this study will be expanded to enroll additional approximately 110 subjects using ORR as the primary study endpoint, to further evaluate the efficacy and safety of ATG-008.

All scans will be collected and then be reviewed centrally for independent analysis of ORR and other objective tumor response outcomes. mRECIST will then also be applied in tumor assessment, if necessary.

Additional details and definitions of response according to RECIST 1.1 are found in Appendix A in Section 19.1.

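### The ORR definitions and the >15% expansion gate do not say whether a response must be confirmed as Section 6.4.1 asks, and the 3-month primary analysis comes before the second scheduled scan.

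*Combined protocol and SAP*

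**What the plan says.** Section 6.4.1 states that subjects with a CR or PR "should have the response confirmed with repeat assessments at the next scheduled scan, but after no less than 28 days".

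The rules that count responders do not mention confirmation:

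- Section 3.1: "ORR: Percentage of subjects with PR, or CR".
- Section 10.3: ORR is "defined as the proportion of subjects with at least a partial response (PR) based on the Treated population subjects".
- Section 10.6.1: "A responder is any subject who achieves a CR or PR".
- The gate, in Section 10.1 and elsewhere: "If ORR of tumor is greater than 15% in the study dose group (45 mg/QD or 20 mg/BID", followed by expansion with about 110 more subjects.

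Appendix A tabulates response at a single time point and has no table for confirmed best overall response. Section 6.4 schedules scans every 8 weeks (± 5 days) from first dose. Section 10.6.1 places the primary ORR analysis about 3 months after the last subject's first dose, with an update at 12 months.

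**The concern.** The trial has no control arm, and success means a lower 95% limit for ORR above 10%. Whether a PR seen once and gone at the next scan counts as a response therefore bears directly on the primary claim. It also bears on the gate, where each subject is worth five percentage points.

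The plan asks for the confirmatory scan but never ties its result to responder status. Two analysts could obtain different ORRs, and different expansion decisions, from the same scans, and the choice could be made after the data are seen. The analysis date makes this worse: for subjects enrolled last, the confirmation that Section 6.4.1 describes will not yet exist.

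**Working it through.** **Plan's own figure.** Inputs from Section 10.3: p0 = 0.10, p1 = 0.18, one-sided 0.025, 80% power, normal approximation.

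n = [(1.960·√(0.10·0.90) + 0.842·√(0.18·0.82)) / 0.08]² = [(0.588 + 0.323) / 0.08]² = 129.8, so 130. The stated sample size reproduces.

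**Success cut-off at N = 130.**

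- Normal-approximation (score) test: 20/130 gives z = (0.1538 − 0.10)/√(0.09/130) = 2.05, above 1.96; 19/130 gives 1.75. The cut-off is at least 20.
- Exact (Clopper-Pearson) limit: 9.66% at 20/130 and 10.29% at 21/130. The cut-off is at least 21.

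Section 10.3 names the normal approximation for sample size. Section 10.6.1 does not name an interval method, so both cut-offs are carried.

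**Gate cut-off.** Section 10.1 plans that "approximately 20 subjects will receive oral ATG-008 at an initial dose of 45 mg/QD and another 20 subjects" will receive 20 mg/BID. With n = 20, 3/20 = 15.0% is not greater than 15% and 4/20 = 20.0% is. The gate is at least 4 responders, so one transient PR can reverse it. This needs no assumed rate.

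**Timing.** Scans fall near days 56 and 112 (± 5). Three months is about day 91.

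- A response first seen on day 56 has its next scheduled scan on day 112. Subjects first dosed within about 112 − 91 = 21 days of the last subject lack that scan at the cut-off.
- A response first seen on day 112 has its next scheduled scan on day 168, so subjects first dosed within about 168 − 91 = 77 days of the last subject could lack confirmation of a response first seen then.
- A repeat scan at exactly 28 days (56 + 28 = day 84) would fit before day 91, but Section 6.4.1 specifies the next scheduled scan.

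**Effect of counting unconfirmed responses.** The documents give no non-confirmation rate, so u = 0, 10%, 20% and 30% are assumed, and the 10% null is taken to be a confirmed rate. A confirmed ORR of 10% is then recorded as 0.10/(1 − u). Binomial tail probabilities:

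| u | Recorded ORR | One group passes gate, P(X ≥ 4 of 20) | P(X ≥ 20 of 130) | P(X ≥ 21 of 130) |
|---|---|---|---|---|
| 0 | 10.0% | 13.3% | 3.4% | 1.9% |
| 10% | 11.1% | 17.5% | 8.3% | 5.1% |
| 20% | 12.5% | 23.5% | 19.2% | 13.1% |
| 30% | 14.3% | 31.8% | 39.7% | 30.6% |

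The columns for 130 are not conditional on passing the gate.

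**The reverse case.** If 18% was meant as an unconfirmed rate but confirmed responses are analysed, the confirmed rate is 0.18·(1 − u) = 16.2%, 14.4% or 12.6%. Exact power falls from 81% to 64%, 41% or 20% (at least 20/130), or from 74% to 54%, 32% or 14% (at least 21/130). So 10.3 needs to say which kind of rate its 10% and 18% are.

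**The case against.** A reader might infer that the plan has decided to count single-scan responses and that the confirmatory scan has no effect on the endpoint. The documents do not support that. No section says an unconfirmed response counts. Section 6.4.1 can be read as the place where best-response rules are kept: the sentence after the confirmation instruction sets a 5-week minimum for SD as a best response. The DCR definition in 10.6.2 does not repeat that minimum, yet nobody would conclude that it is void. On that reading, achieving a PR in 10.6.1 means a confirmed PR. Appendix A calls itself a summary of the published criteria and refers the reader to them, and Section 10.1 defers final methods to a statistical analysis plan. The appendix's silence therefore proves little.

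The inflation figures are also conditional. If 10% and 18% are both unconfirmed rates, counting unconfirmed responses leaves the error at 1.9% (or 3.4%) and nothing is inflated. Duration of response and the 12-month update would make short-lived responses visible, although they could still be counted.

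These points defeat the firm reading. The ambiguity remains. Section 6.4.1 says should, gives no category for a response that fails confirmation, and is not cited by any responder rule. The 3-month date does not fit a confirmed endpoint for late-enrolled subjects. Deferring detail to a later analysis plan does not settle the gate, which is a decision rule of the protocol itself.

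**Conclusion.** The point holds as an unresolved ambiguity in the primary endpoint and the go/no-go rule, combined with an analysis date too early for confirmation in late-enrolled subjects. It is not an explicit decision to count unconfirmed responses, and the sample size is not in error.

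The gate's sensitivity to a single response is certain with 20 subjects per group. The false-positive figures are scenarios. They rest on assumed non-confirmation rates of 10% to 30%, on the 10% null being a confirmed rate, and on the cut-off used. Within that range the chance of reaching the final cut-off at a confirmed ORR of 10% is 5.1% to 30.6% (exact limit) or 8.3% to 39.7% (normal approximation), against a nominal 2.5%. This should be corrected before the gate is read.

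**What to change.** - In 3.1, 10.3, 10.6.1 and every statement of the gate, define a responder as a subject with a CR or PR confirmed at least 28 days later, as 6.4.1 describes.
- State how a CR or PR that is not confirmed is classified.
- Report ORR including unconfirmed responses as supportive only.
- State in 10.3 that 10% and 18% are confirmed rates.
- Set the gate reading and the primary ORR cut-off beyond the last subject's week-16 scan, and wait until any response first seen at that scan has been re-scanned. Requiring confirmation without moving the 3-month date would count true late responders as non-responders and bias ORR downward.

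Cost: a later gate and primary analysis, and possibly a lower reported ORR. N stays at 130, and no extra scans are needed because 6.4 and 6.4.1 already call for them.

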Blood samples will be collected for intensive sampling in all 30 subjects in order to estimate the PK of ATG-008 and metabolites in Asian subjects.

As for the 2 dose groups 45 mg/QD and 20 mg/BID, PK samples of 10 subjects each should be collected to further evaluate the PK profile of ATG-008 and its metabolites.

Overview of Exposure-Response Analyses

Exposure-response analyses will be performed to evaluate relationships between ATG-008 and/or M1 exposure and clinical outcomes of efficacy and safety.

Statistical Summary

The primary efficacy endpoint is ORR, and the primary analysis population for both efficacy and safety analysis is the Treated population.

All efficacy and safety results will be tabulated and/or summarized using for the Treated population by treatment arm.

TABLE OF CONTENTS

MEDICAL / EMERGENCY CONTACT INFORMATION.....	2
PROTOCOL SYNOPSIS.....	5
TABLE OF CONTENTS.....	12
LIST OF TABLES	15
LIST OF FIGURES.....	15
1. INTRODUCTION	20
1.1. Hepatocellular Carcinoma	20
1.2. Mammalian Target of Rapamycin	22
1.2.1. Hepatocellular Carcinoma and mTOR.....	22
1.3. ATG-008.....	23
1.3.1. ATG-008 Preclinical Data.....	23
1.3.2. ATG-008 Clinical Data	25
1.4 Study Rationale.....	31
1.4.1 Rationale for Dose of ATG-008	32
2. STUDY OBJECTIVES	34
2.1 Primary Objective	34
2.2 Secondary Objectives.....	34
3. STUDY ENDPOINTS	34
3.1 Primary Endpoint.....	34
3.2 Secondary Endpoints	34
4. OVERALL STUDY DESIGN	34
4.1 Study Design.....	34
4.2 Study Design Rationale.....	36
4.3 Study Duration	37
4.4 End of Trial	38
5. TABLE OF EVENTS.....	39
6. PROCEDURES.....	43
6.1. Screening Period	43
6.2. Treatment Period.....	45
6.2.1 End of Treatment.....	46
6.3. Follow-up Period	46
6.3.1 28-day Follow-up.....	46
6.3.2 Efficacy Follow-up	46
6.3.3 Survival Follow-up	46
6.4. Response Assessments	46
6.4.1 Assessment of Radiologic Response According to RECIST 1.1	47
6.5. Pharmacokinetics	47
6.5.1 Intense Blood Sampling.....	48
6.5.2 PK urine collection	48
7. STUDY POPULATION	49
7.1 Number of Subjects.....	49
7.2 Inclusion Criteria	49
7.3 Exclusion Criteria	50
8. DESCRIPTION OF STUDY TREATMENTS.....	52
8.1 Description of Investigational Product(s)	52
8.2 Treatment Administration and Schedule	52

8.2.1	Treatment modification	52
8.2.2	Overdose	54
8.3	Method of Treatment Assignment	54
8.4	Packaging and Labeling	54
8.5	Investigational Product Accountability and Disposal	54
8.6	Investigational Product Compliance	55
9.	CONCOMITANT MEDICATIONS AND PROCEDURES	55

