Meanwhile, the PK profile of this study was similar to the PK profile of foreign patients

(indicating that PK profile of ATG-008 showed linear relationship). Based on the clinical observation results, low dose of ATG-008 can achieve steady state plasma concentration at which the drug exert effect, indicating that the administration mode of BID at a low dose may have certain advantage on maintaining effective steady state concentration compared to the administration mode of QD.

According to the above bases, this study proposes to add 2 dose groups, i.e., 45 mg/QD and 20 mg/BID (approximately 20 subjects each), to further explore and evaluate the PK, safety, tolerability and efficacy of ATG-008 in advanced HBV+ HCC subjects.

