4. OVERALL STUDY DESIGN

4.1 Study Design

ATG-008-HCC-001 is a MRCT trial in which ATG-008 will be administered orally in HBV+ HCC subjects who have received at least one prior line of systemic therapy in Asian countries. The trial is designed as an open-label phase 2 trial to assess PK, safety, tolerability and efficacy of oral ATG-008 administered until the appearance of radiologic disease progression (according to RECIST 1.1). The PK and safety profiles will be compared with historical ATG-008 results when

data are available.

According to the previous study results, the sponsor will plan to continue to enroll approximately 40 hepatitis B virus (HBV) positive, unresectable HCC subjects who have previously received at least one prior line of systemic therapy. Among which, approximately 20 subjects will receive oral ATG-008 at an initial dose of 45 mg/QD and another 20 subjects will receive oral ATG-008 at an initial dose of 20mg/BID. The pharmacokinetic (PK) samples will be collected from 10 subjects each in the two dose groups so as to further evaluate the PK profile of ATG-008 and its metabolites.

If the overall response rate (ORR) of tumor is greater than 15% in the study dose group (45 mg/QD or 20 mg/BID), then this study will be expanded to enroll additional approximately 110 subjects using ORR as the primary study endpoint, to further evaluate the efficacy and safety of ATG-008.

At the discretion of the Investigator, treatment may continue beyond radiologic progression until symptomatic deterioration if no other therapeutic options are available. Subjects may also receive best supportive care according to local practice. All subjects will continue to be followed after treatment discontinuation for radiologic tumor response until disease progression, death or withdrawal of consent (as defined in Section 6.4, if applicable) and new anticancer treatments until death or withdrawal of consent. Subjects will also be followed for survival until death or withdrawal of consent.

[figure not shown]
The starting dose of ATG-008 will be 15 mg daily for 28 days each cycle for the first 6 fully evaluable (including PK outcomes) subjects. Providing DLTs occur in less than 2 of 6 subjects who complete Cycle 1, additional 24 subjects will be enrolled at the starting dose of 30 mg daily. Subjects who tolerated the 15-mg dose level for at least 1 cycle may then dose-escalate to 30 mg at the Investigator's discretion.

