8.3 Method of Treatment Assignment

Subjects who are in the first part of this study and are enrolled into screening period will be assigned with one available subject number. The assignment to cohort of 15mg or 30mg will be in sequence.

As for approximately 40 HCC subjects who are planned to be enrolled, subjects will be randomly assigned with one available subject number during screening period to receive oral ATG-008 at an initial dose of 45 mg/QD or 20 mg/BID.

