10.2 Study Population Definitions

10.2.1 Treated Population

The Treated population will consist of all enrolled subjects who received at least one dose of study drug. It is equivalent to the Safety population. The Treated population will be used for the primary efficacy and safety analyses for this single arm Phase 2 study. Treated population will be used (instead of Safety population) for the rest of the protocol.

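### The 45 mg/QD and 20 mg/BID arms are randomised, but no between-arm estimate is planned, and by-arm tables after a one-dose expansion favour the expanded dose on average

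*Combined protocol and SAP*

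**What the plan says.** Assignment (8.3): for the added cohort, "subjects will be randomly assigned with one available subject number during screening period to receive oral ATG-008" at one of the two starting regimens. Section 10.1 gives the sizes: "approximately 20 subjects will receive oral ATG-008 at an initial dose of 45 mg/QD and another 20 subjects" at 20 mg/BID.

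Expansion (10.1, repeated in 4.1, 4.2, 6.4.1 and 7.1): an observed ORR above 15% in a dose group leads to about 110 more subjects.

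Primary analysis (10.3, 10.6.1): ORR is "tested using one sample binomial test for the Treated population", with a null of 10% and an alternative of 18%. The 130 subjects are made up as 20+110, so the subjects who met the gate are counted again in the final analysis.

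Design label (10.2.1): "The Treated population will be used for the primary efficacy and safety analyses for this single arm Phase 2 study".

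Comparison and display: the one comparison named in 4.1 is external: "The PK and safety profiles will be compared with historical ATG-008 results when" those data exist. In the synopsis (Statistical Summary), "All efficacy and safety results will be tabulated and/or summarized using for the Treated population by treatment arm"; 10.7 repeats this for safety. Nothing in 10.1 to 10.7 estimates a difference between the two randomised regimens. The secondary endpoints in 10.6.2 are defined without a contrast, the subgroups in 10.6.3 are baseline factors, and the exposure-response work in 10.6.5.2 is exploratory and is not a contrast of regimens.

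**The concern.** Randomisation gives the two dose groups of about 20 a fair comparison with each other, and the plan never takes it. The regimens meet only in the by-arm tables.

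Once a single dose expands, those tables no longer show a randomised comparison. One column holds 20 subjects kept because their response rate was high, plus about 110 later subjects. The other holds 20 subjects who, if only one dose passed, are there because their response rate was low. Two equally active regimens would then differ on paper because of the gate. A reader choosing between QD and BID dosing from that table could be misled, although unbiased data from the same trial would exist.

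**Working it through.** **The plan's own figure.** One-sample normal approximation, 10% vs 18%, one-sided 0.025, 80% power (10.3):

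n = [(1.960·√(0.10·0.90) + 0.842·√(0.18·0.82)) / 0.08]² = 129.8, so 130. Power at 130 is 80.1%. The stated size reproduces.

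**Inputs for the display.** Two arms of exactly 20 (10.1); gate of observed ORR above 15%, hence at least 4/20, since 3/20 = 15.0% does not pass; 110 added to the expanded arm (10.3); the same true rate p in both arms and throughout. I use p = 10% and 18% from 10.3 and 15% from the gate.

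**Exactly one dose passes.** With X ~ Bin(20, p) and P = Pr(X ≥ 4):

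- expanded arm = (E[X | X ≥ 4] + 110p) / 130
- unexpanded arm = E[X | X ≤ 3] / 20
- Pr(exactly one passes) = 2P(1 − P)

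| | p = 10% | p = 15% | p = 18% |
|---|---|---|---|
| P | 13.3% | 35.2% | 49.7% |
| Pr(exactly one passes) | 23% | 46% | 50% |
| Passing 20, mean ORR | 22.2% | 23.8% | 25.0% |
| Expanded arm of 130, mean ORR | 11.9% | 16.3% | 19.1% |
| Unexpanded arm of 20, mean ORR | 8.1% | 10.2% | 11.1% |
| Gap, points | +3.7 | +6.1 | +8.0 |
| Pr(expanded arm shows higher ORR) | 71% | 87% | 95% |

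Example at 18%: (20·0.2501 + 110·0.18)/130 = (5.00 + 19.80)/130 = 19.1%, against 11.1%. For an unselected 130 vs 20, the last row would be about 51% to 52%. A simulation at 15% gave 16.35% vs 10.22%, matching the exact result.

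The gap has two sources. Carrying the passing 20 into the 130 adds 1.9, 1.4 and 1.1 points. Conditioning the unexpanded arm on at most 3/20 adds 1.9, 4.8 and 6.9 points.

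**Both doses pass, one expands.** If the higher arm is chosen, the gap is −8.5, −4.6 and −2.5 points at 10%, 15% and 18%. The unexpanded arm is now itself selected for at least 4/20 and is not diluted. Given any expansion, both pass 7%, 21% and 33% of the time.

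**Averaged over all one-dose expansions.** The gap is +2.9, +3.8 and +4.5 points if the higher arm is chosen when both pass, and +2.7, +3.2 and +3.4 if the choice is random. Check at 18%, higher chosen: (0.500·8.01 − 0.247·2.55)/0.747 = 4.5.

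**What the randomised contrast gives.** Under equal doses, the expected 20 vs 20 difference is 0. Its approximate 95% CI half-width, 1.96·√(2p(1−p)/20), is 18.6, 22.1 and 23.8 points. If it were reported only when exactly one arm passes, it would carry a bias of 14.0, 13.6 and 13.9 points. It therefore has to be reported unconditionally.

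For PK with 10 per arm, the 90% CI factor for a geometric mean ratio is exp(1.734·√ln(1+CV²)·√(2/10)): 1.26 at a between-subject CV of 30% and 1.44 at 50%. Both CVs are assumptions. Section 6.5.1 samples Day 15 over 24 h for QD and 12 h for BID, so the ratio needs a common interval.

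**The case against.** The strongest reply is that no objective goes unmet. Sections 2 and 3 ask for PK, safety, tolerability and ORR to be evaluated, not compared across regimens. Randomising between doses that are each judged against a fixed rate is an accepted non-comparative use of randomisation. That stands, and it is why the one-sample test should remain primary. The plan does not, however, declare the randomisation non-comparative, and the single-arm label in 10.2.1 does not fit 8.3.

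Two stronger readings are tempting and fail:

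- A reader might infer that 1.4.1 makes QD versus BID the question of the second part, since it contrasts BID with once-daily dosing: "the administration mode of BID at a low dose may have certain advantage on maintaining effective steady state concentration compared to the administration mode of" once-daily intake. This is background rationale. The purpose stated next is to explore and evaluate each added dose.
- A reader might suppose that the 80% in 10.3 would be taken as power to compare the doses. That section names a one-sample test, a 10% null and 20+110 subjects, so the risk is not real and no statement of between-arm power is needed.

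Other points stand in part. The synopsis (Length of Trial) and 4.3 plan an evaluation of the roughly 40 subjects, and the gate needs ORR by dose, so unselected 20 vs 20 data will exist before expansion; what is missing is a planned estimate of the difference. If neither dose passes (75%, 42% and 25% of the time at 10%, 15% and 18%), the final table for these two arms is a clean randomised one. Section 10.7 already tabulates safety and dose modifications by arm, though with no difference or interval. Section 10.1 defers detail to a separate SAP, which is not in the supplied text and could contain a contrast.

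**Conclusion.** The point holds as a cheap improvement. It is not a fault in the primary test. The plan randomises about 40 subjects, estimates no difference between their arms, and would display a gate-selected comparison after a one-dose expansion. With equal true ORR, the display favours the expanded dose by 3.7 to 8.0 points when exactly one dose passes and by 2.7 to 4.5 points averaged over all one-dose expansions. At the upper end, that equals the 8-point effect (10% to 18%) the trial is sized to detect.

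A reader might infer that the expanded dose always looks better. It does not: this is an average, and it reverses at these rates when both doses pass and only the higher expands. If both doses expanded, this bias would not arise between them. The plan settles neither case.

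The figures assume exactly 20 per arm, 110 added and a constant true rate. They cover ORR only and leave out any drift among the later 110, whose allocation the plan does not describe.

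**What to change.** 1. In 10.6 and 10.7, pre-specify a descriptive estimate in the roughly 40 randomised subjects only, at a data cut fixed in advance, reported whatever the gate outcome and excluding expansion subjects. Give the 45 mg/QD minus 20 mg/BID difference in ORR, in the rate of dose reduction or interruption, and in the rate of Grade 3 or higher related TEAEs, each with a 95% CI. Add a geometric mean ratio of steady-state exposure with a 90% CI over a common interval, for example 24-hour exposure with BID taken as twice AUC0-12. State how the 10 PK subjects per arm are chosen, since 6.5.1 does not.
2. In by-arm tables after expansion, put the randomised 20 and the expansion 110 in separate columns.
3. In 10.2.1, replace the single-arm label with wording that the second part has two randomised dose arms, each tested against a fixed rate.

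The cost is protocol and SAP wording and a few tables, with no added subjects, visits or samples. The drawback is precision: the ORR interval has a half-width of about 19 to 24 points and must be labelled as estimation, not a test of superiority.
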